2.2 Setting and Participants

2.2.1 Setting:

The study will be conducted in Cardiff and Vale University Health Board, with patients drawn from Cardiology clinics and inpatient wards. Follow-up assessments will be conducted at Cardiff School of Sport, a research facility at a university campus close to the main hospital.

2.2.2 Number of subjects planned:

10 patients. This will be sufficient to establish estimates of variability in the diastolic reserve index (see below), allow estimation of treatment difference and gauge acceptability.

2.2.3 Target population:

Subjects with HFpEF and chronotropic incompetence

2.3 Endpoints:

Systolic and diastolic longitudinal reserve index are calculated by the following formulae:

$$\begin{aligned}\text{Systolic reserve} &= \Delta s' \times [1 - (1/s'_{\text{rest}})] \\ \text{Diastolic reserve} &= \Delta e' \times [1 - (1/e'_{\text{rest}})]\end{aligned}$$

These are known to be impaired in patients with HFpEF and are a marker of adaptation to exercise in terms of filling pressures and left ventricular relaxation. Tan et al report a significant difference between the results seen with 56 patients with HFpEF and 27 control subjects on exercise echocardiography with semi-supine bicycle.¹⁶ Patient characteristics were similar to those of our proposed study group (EF >50%, NYHA II, HFpEF according to Vasan and Levy criteria).²⁸

We will therefore investigate diastolic and systolic reserve index as possible endpoints of a future study into the efficacy of CRT versus RRP in HFpEF patients.

2.4 Planned interventions:

Visit 1 – Baseline Assessments: Patients will undergo initial assessment of baseline characteristics by echocardiography, cardiopulmonary exercise testing, 6MWT and MLHFQ. (Visit length: approx. 4 hours)

Visit 2 - Device Implantation (≤ 7 days after baseline assessments completed): Eligible subjects will undergo implantation of a biventricular pacemaker under normal laboratory conditions. Patients will be randomised in a 1:1 ratio to receive either rate-responsive pacing (DDDR) or CRT. Patients will be blinded to their treatment allocation. They will return to pacing clinic a week later for a programming check; during this visit, they will also undergo a chest x-ray according to local protocol to ensure correct lead placement (Visit length: 1 day + 2 hours)

Visit 3 – Assessments and Device Reprogramming

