3.2 Study Extension: Targeted Multipoint Pacing

Once all subjects have completed 12 weeks of RRP and 12 weeks of CRT (in either order), provisional analysis of the data will be performed. If an incremental benefit is shown for CRT above the benefit of RRP, analysis of echocardiograms before and after CRT will be performed to elucidate the mechanisms. Subjects will be invited to participate in a study extension. The pacemakers will then be non-invasively programmed using multisite optimisation to administer optimised CRT targeted to the specific mechanism of action. Final assessments will occur after 12 weeks, following which the participant involvement will end.

If no incremental benefit is shown for CRT at the initial analysis, the study will end at this point (after 24 weeks).

Incremental benefit for CRT will be defined as a statistically significant difference between average values for RRP and for CRT in paired t-tests in one or more of the following parameters: a) echocardiographic: diastolic reserve index; systolic reserve index; left ventricular end-systolic volume; left ventricular end-diastolic volume; tricuspid regurgitant peak velocity; torsion and untwisting on strain imaging; global longitudinal strain; b) cardiopulmonary exercise testing: peak oxygen consumption; exercise duration; VE-VCO₂ slope; c) distance walked on 6-minute walk test.

Ongoing pacemaker function will be a clinical decision based on patient preference and objective markers such as 6MWT. Long-term pacemaker follow-up will take place at [name] CRT clinic at University Hospital of Wales. All medications can be continued as prescribed for the duration of the study, but medication changes should be noted during follow-up.

4. Criteria for Evaluation

At each 12-week stage, the following will be assessed:

1. Change in end-diastolic volume
2. Change in end-systolic volume
3. Change in ejection fraction (Simpson's Biplane method)
4. Change in left ventricular filling by pulsed-wave Doppler of mitral inflow (peak E and A wave velocities, E wave deceleration time, A wave duration, diastolic filling time (DFT))
5. Change in pulmonary venous Ar (Atrial reversal) duration.
6. Change in left and right ventricular isovolumic relaxation time (IVRT) and isovolumic contraction time (IVCT)
7. Change in peak diastolic suction velocity (V_p)
8. Change in peak systolic twist (torsion) and in untwisting rate on speckle tracking

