9. Myocardial velocity imaging (MVI) in basal anterior, inferior, septal and lateral walls to assess:
 - a. Change in peak systolic velocity (s')
 - b. Change in peak early diastolic wave velocity (e')
 - c. Change in time from onset of QRS to onset of s' wave
 - d. Change in time from onset of QRS to peak e' wave
10. Change in duration of pulmonary venous a wave
11. Change in peak longitudinal strain in 12 wall segments, and peak global longitudinal strain (GLS) in 12-segment model
12. Change in pulmonary pressures as measured by tricuspid regurgitant jet peak velocity
13. Change in above parameters on exercise echocardiography where feasible due to image quality
14. Change in peak oxygen consumption (VO_2 max) and slope of ventilation to carbon dioxide production (VE- VCO_2 slope) on exercise
15. Change in exercise capacity as defined by duration of exertion and work-level achieved on cardiopulmonary exercise testing
16. Change in blood pressure response to exercise
17. Change in distance walked on 6-minute walk test
18. Change in New York Heart Association Functional Class
19. Change in Minnesota Living with Heart Failure Questionnaire score

5. Statistical Analysis Plan

Enrolled subjects will be analysed in a per protocol fashion. Estimates of period effects will be made by performing an unpaired t-test on the mean difference between the two treatment orders. Carryover effects will be estimated by performing a t-test comparing the mean within patient score (the mean of the two period means for each patient) with the mean between the treatment arms. If significant period or carry-over effects exist, then only the first period will be analysed.

The change in exercise, echocardiographic, functional class and wellbeing parameters will be evaluated using paired sample t-tests. A Wilcoxon signed rank test will be employed as a test of robustness.

The settings in the study extension will be compared with the CRT programming during the initial crossover period for each patient using paired sample t-tests (this may have taken place in period 1 or period 2).

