Where normality of distribution is not found, attempts will be made to transform the data using a suitable mathematical function. Where this is not possible, the Mann-Whitney U test will be employed. Analysis of categorical data will be by Chi-squared tests. Normality will be evaluated using visual assessment histograms and Q-Q plots. Significance will be tested at the 95% confidence level for all analyses, including calculation of period and carry-over effects.

An intention to treat analysis will be reported if the drop-out rate exceeds 10%. Corrections for multiplicity will not be made due to the exploratory nature of this data. No subgroup analysis is planned. Where data is missing, analysis will only be completed if 80% or more of data is present. For each analysis performed, subjects with data missing will be excluded from the individual parameter analysis, but will be included where data is present. Interim analysis will not be performed, except in the event of study discontinuation. Study discontinuation will occur only in the event of safety concerns, as detailed below, or in the event of failure to recruit within the planned timeframe.

Drop-out rates and reasons will be recorded at each stage. This will be presented as a CONSORT diagram in the publication of study results.

All statistical analysis will be double-checked by a statistician prior to dissemination of study results.

6. Study Administration

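### A test that yields no value because the patient was too symptomatic on one pacing mode is dropped like any other missing value, which biases that comparison towards the mode that caused the inability

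*Combined protocol and SAP*

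**What the plan says.** Section 5 sets a parameter-by-parameter complete-case rule: "For each analysis performed, subjects with data missing will be excluded from the individual parameter analysis, but will be included where data is present". The one limit is on quantity: "Where data is missing, analysis will only be completed if 80% or more of data is present". Neither sentence refers to the reason a value is missing. The main analysis is per protocol. An intention-to-treat analysis is promised if drop-out exceeds 10%, but no value is assigned to a missing result. The check on the t-test is: "A Wilcoxon signed rank test will be employed as a test of robustness". No separate missing-data handling is given for it.

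Section 3.2 says what the comparison decides: "Incremental benefit for CRT will be defined as a statistically significant difference between average values for RRP and for CRT in paired t-tests". A significant result on any single listed parameter is enough. Those that need an exercise or walk test are peak oxygen consumption, exercise duration and VE-VCO₂ slope ("cardiopulmonary exercise testing: peak oxygen consumption; exercise duration" and the item after it), the 6-minute walk distance, and the systolic and diastolic reserve indices, which section 2.3 builds on the change in s' and e' with exercise. NYHA class and the MLHFQ score are collected (section 4) but are not in the benefit definition.

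**The concern.** In a crossover trial of two pacing modes in breathless patients, a missing exercise result may itself be information about the mode. A patient too symptomatic on CRT to attempt the walk has done badly on CRT. The rule removes that patient's pair, so the mode is judged only on those who could be tested on both.

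The built-in checks do not restore the lost pair. The Wilcoxon test runs on the same reduced set. The 80% floor counts missing values without asking why they are missing. One drop-out in 10 is exactly 10% and does not exceed the intention-to-treat trigger, and a patient who attends but cannot exercise need not be a drop-out at all. Drop-out reasons go into the CONSORT diagram and not into the benefit rule.

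Two things are at stake: the finding that opens the 12-week extension, and the treatment-difference estimates meant to inform a later trial.

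**Working it through.** **Inputs from the documents.** Sample size: "10 patients. This will be sufficient to establish estimates of variability in the diastolic reserve index". Each patient receives both modes, so there are at most 10 pairs. No power calculation, effect size or SD is given, so there is no planned figure to reproduce. Significance level: "Significance will be tested at the 95% confidence level for all analyses", taken here as two-sided 5% per test. Section 3.2 does not state a direction, so benefit is counted below only when the significant difference favours CRT.

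**How many pairs can go.** 0.8 × 10 = 8, so two patients can be missing and the parameter is still tested. If the 80% is counted in patient-period values, 0.8 × 20 = 16. Four patients could then each lack one value, leaving six pairs.

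**Assumptions, because the documents give none.** CRT minus RRP differences are normal with SD 1. One or two patients have mean -2 SD and yield no value on CRT. The others have mean 0, +0.5 or +1 SD. The test is t = mean/(SD/√n) against the two-sided 5% point: 2.262 for 10 pairs, 2.306 for 9 and 2.365 for 8. There were 200,000 simulated trials per case.

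| Unable on CRT | Mean in the others | True mean of all 10 | Significant for CRT, pairs excluded | Significant for CRT, all kept |
|---|---|---|---|---|
| 2 | +0.5 | (8 × 0.5 - 2 × 2)/10 = 0 | 23% | 0.3% |
| 1 | +0.5 | (9 × 0.5 - 2)/10 = +0.25 | 26% | 4% |
| 2 | +1.0 | (8 × 1 - 2 × 2)/10 = +0.4 | 68% | 3% |
| 1 | +1.0 | (9 × 1 - 2)/10 = +0.7 | 75% | 24% |
| 2 | 0 | (0 - 2 × 2)/10 = -0.4 | 2.5% | under 0.1% |

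Two cautions on reading the table. First, the 0.3% lies below the nominal 2.5% partly because the two low values inflate the SD: expected sample variance = 1 + (8 × 0.5² + 2 × 2²)/9 = 2.11, so SD is about 1.45 instead of 1. Against the nominal 2.5%, 23% is still about nine times too high when the true mean is zero. Second, when the others gain nothing (last row), exclusion only returns the nominal rate. What is lost there is the chance of seeing the harm: a significant result against CRT falls from 8.4% to 2.5%.

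**Upper bound with no true effect.** If the missing pairs happened to be the lowest differences of the 10, a false finding for CRT would rise from 2.5% to 8.6% (one dropped) or 18.6% (two dropped).

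**What keeping the pairs does to the rank tests** (exact, two-sided, every tested patient better on CRT):

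- Wilcoxon, one unable: excluded, 2/2⁹ = 0.0039. Kept at rank 10, 43 of 1,024 sign patterns have a negative rank sum of 10 or less, so p = 2 × 43/1,024 = 0.084.
- Wilcoxon, two unable: excluded, 2/2⁸ = 0.0078. Kept at ranks 9 and 10 (sum 19), p = 2 × 221/1,024 = 0.43, or 0.42 if the two are tied at 9.5.
- Sign test, pairs kept: 9 of 10 gives 2 × (1 + 10)/1,024 = 0.021; 8 of 10 gives 2 × (1 + 10 + 45)/1,024 = 0.109.

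**The case against.** The strongest reply is that the case is narrow and the stakes are low. A patient who starts and stops early still yields a distance, a duration and usually a peak oxygen consumption, and these count against the mode. Entry requires the ability to complete a cardiopulmonary exercise test, and section 2.5 describes patients as stable over the period. The Appendix lowers the exercise-echo workload so that imaging can finish, and section 4 names image quality as what limits that test. The primary objective is feasibility, the benefit finding opens only an optional extension, and NYHA class and MLHFQ are still analysed. All of this stands. It limits how often the problem can arise and how much follows from it, but it does not supply a rule for a test that yields no value.

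A reader might infer more than the documents support:

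- That harm leaves only the CRT average. In a paired test the patient leaves both averages; what is lost is the unfavourable difference.
- That the rule favours CRT. It is symmetric: inability on RRP would bias the result against CRT.
- That all three groups of benefit parameters depend on exercise. In the echocardiographic group only the two reserve indices inherently do. Volumes, tricuspid velocity, torsion and strain can be measured at rest.
- That a significant result in half to three quarters of trials, when 8 or 9 tested patients gain 0.8 to 1.0 SD, measures the bias. That is ordinary power, and with all 10 pairs at those effects it is higher (62% and 80%). The bias shows only in the contrast between excluding and keeping the same patients.

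**Conclusion.** The point holds in a limited form. The plan has no rule for a walk, cardiopulmonary or reserve-index result that is absent because the patient was too symptomatic on one mode. Complete-pair exclusion then biases that parameter towards the mode responsible. Under the assumed effects (two of 10 at -2 SD, the rest at +0.5 SD) the chance of a CRT benefit finding on one parameter is about 23% instead of about 0.3%. With one such patient it is about 26% instead of 4%, although there the true mean is +0.25 SD and not zero. These sizes rest on assumed effects and on at least one patient yielding no value; the documents give no rate for that. The consequence is confined to an exploratory benefit finding, the opening of the extension and planning estimates for a later trial. This is a cheap improvement and not a flaw that undermines the study.

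**What to change.** In section 5:

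1. Record a reason for every walk, cardiopulmonary test or exercise echocardiogram that yields no value, separating symptoms from image quality and logistics.
2. Report, by parameter, the number unable for clinical reasons on CRT and on RRP.
3. Beside the complete-pair t-test, report a sensitivity analysis that keeps those pairs scored as favouring the other mode, using a sign test and a worst-rank Wilcoxon.
4. State in the incremental-benefit conclusion whether the result survives it.

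Do not make the sign test a condition for benefit. Required only to agree in direction, it changes almost nothing: with two unable and the other eight at 0.8 SD, declared benefit moves from about 50% to about 49%. Required to reach 5%, it cuts power with complete data at 0.8 SD from 62% to 33%, and with two unable on CRT it cannot be met at all (8 of 10 gives p = 0.109).

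The cost is a reason code on the case record form and a few lines of SAP text. There are two downsides. With 10 pairs the smallest worst-rank Wilcoxon p is 0.084 with one unable on CRT and about 0.43 with two, so this is a sensitivity check and cannot replace the planned test. The reason is also coded by investigators who know the pacing mode (section 3), so the code list and the moment of coding should be fixed in advance.

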6.1 Resources

The study will be carried out principally by [name], the principal investigator, who is employed by the health board and funded by St Jude Medical (now Abbott). Eligibility assessments required for the study are part of the usual care for patients with heart failure and will therefore be conducted at University Hospital of Wales under the NHS.

Baseline assessments, follow-up appointments, echocardiography, cardiopulmonary exercise testing, questionnaires and functional tests will be carried out by [name] and research staff from the School of Sport, Cyncoed Campus, Cardiff Metropolitan University. This will be overseen by prior agreement with [name]. Device implantation will be conducted by [name] in the Pacing Theatre at University Hospital of Wales on normal clinical lists, usually on a Tuesday. Abbott will pay for the difference in device cost between a dual chamber and a biventricular device. A member of nursing staff from the coronary care unit will be required to assist in these procedures and this will be arranged prior to implantation. Patients recruited to the study will be under a consultant at the hospital and will have a Class IIb indication for pacing.

6.2 Ethical Considerations

Patients recruited to this study will have an indication for a dual chamber pacemaker and significant symptoms of breathlessness. Full written consent will be obtained prior to study entry. Patients will be exposed to a small increase in risk due to implantation of a biventricular rather than dual chamber pacemaker. This equates to an increase from 1% to 2% of serious complications requiring further hospital treatment. This risk is felt to be acceptable in patients with reduced ejection fraction undergoing biventricular pacemaker implantation. Additionally, there will be extra radiation exposure due to longer procedure

time associated with CRT implantation compared with standard pacemakers. These risks have been reviewed by experts in clinical radiology and nuclear physics. The overall exposure to radiation is equivalent to 21 months of background radiation in the UK and confers a low cancer risk of 1 in 5100. Exercise tests are low risk procedures conferring overall risk of 1 in 10 000 of serious complication. Subjects will be counselled regarding these procedures prior to recruitment.

6.3 Safety

Local procedures will apply to tests carried out at University Hospital of Wales, and to pacemaker implantation. A local anticoagulant policy is in place. Patients will receive intravenous antibiotics prior to pacemaker implantation according to local policy (usually Teicoplanin).

All investigations at Cardiff Metropolitan University will take place in the presence of an experienced clinician. Other members of staff will be available who have been trained in Intermediate Life Support. A cardiac defibrillator, supplemental oxygen and intravenous adrenaline will be available. Additionally, there will be equipment for cannulation and airway support that will be kept in an easily accessible bag within the department. These products and medications will be checked on a monthly basis by study staff.

6.3.1 Adverse Events

Early termination will occur in the case of serious adverse events (SAE) related to study interventions. If a SAE occurs (death or hospitalisation of study subject for heart failure or related conditions, device related complications), the study team will meet at the earliest possible juncture. A decision as to whether adverse events are related to study procedures will be made according to clinical judgement by the study group, which includes several experienced clinicians.

If the SAE is deemed to be due to the study intervention, the trial will be immediately suspended pending further investigation and terminated if evidence emerges of causality. In the event of study suspension, all participants will be contacted to explain the situation and will be asked to attend for reprogramming of their pacemaker as appropriate.

In the event of early study termination, all participants will be contacted by telephone and asked to attend for device reprogramming. Devices will be programmed to RRP on study termination unless safety issues arise with this programming mode.

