1.1 Background and Rationale

Half of patients with the clinical syndrome of heart failure have normal ejection fraction. Their cardiovascular mortality is similar to those with reduced ejection fraction (including 26% sudden cardiac death, 14% heart failure and 5% myocardial infarction).¹

The hallmark of Heart Failure with Preserved Ejection Fraction (HFpEF) is exercise intolerance. The mechanisms for this include impaired left ventricular active relaxation, impaired untwisting and torsion, reduced left ventricular suction, increased passive stiffness, dyssynchrony, impaired systolic and diastolic reserve, increased arterial stiffness and impaired peripheral oxygen utilisation, among others. Chronotropic incompetence is a contributor to this, affecting up to 63% of patients.² Despite the prevalence of impaired chronotropy, it is little recognised in clinical practice.

Exercise endurance training has been shown to increase peak heart rate in patients with chronotropic incompetence and heart failure by an average of 12 beats per minute.³ Additionally, such training programmes improved peak oxygen utilisation on exercise testing

by 38% and self-reported physical functioning score by 50% in HFpEF.⁴ However, in practice exercise programmes are difficult to coordinate and maintain. Use of rate-responsive pacing improved peak oxygen consumption by 18% in heart failure patients with proven chronotropic incompetence undergoing cardiac resynchronisation therapy (with reduced ejection fraction).⁵ The RESET trial is currently recruiting and aims to evaluate the effect of rate responsive pacing on patients with HFpEF;⁶ currently, chronotropic incompetence is a Class IIb indication for dual-chamber pacing.

No trial of drug therapy in HFpEF has yet shown symptomatic or outcome benefit, although there is some evidence of improved diastolic and longitudinal function with valsartan (VALIDD),⁷ amlodipine (ASCOT),⁸ nebivolol (ENESYS)⁹ and spironolactone (TOPCAT),¹⁰ all except the latter were conducted in hypertensive patients rather than HFpEF.

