- Cardiopulmonary exercise testing on an upright bicycle according to standard local protocol (see above).

Study subjects will then undergo implantation of a biventricular pacemaker with leads in the right ventricular apex, coronary sinus (aiming for posterolateral or lateral wall position where anatomically possible), and right atrium.

Following successful device placement, subjects will be randomised in a 1:1 ratio (using online computer randomisation software, <https://www.randomizer.org/>) to receive either RRP (in DDDR mode) or CRT as described above. This will be performed whilst the subject is still in the pacing laboratory and the device programmed by the attending physiologist according to the parameters described above, tailored to the subject's individual heart rate. Patients will be blinded to the treatment allocation, but investigators will not as the pacing mode will be evident on ECG traces.

3.1 Assessments and Reprogramming:

After 12 weeks, patients will be recalled for repeat assessment of the same modalities (rest and exercise echocardiography, CPEX, 6MWT, NYHA functional class assessment, MLHFQ). The pacemakers will be non-invasively reprogrammed (using a magnet placed over the chest) to switch the treatment period so that subjects experience whichever mode they have not yet received. After a further 12 weeks, the same assessments will be repeated. The pacemaker will then be non-invasively programmed back to RRP.

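### The SAE definition in 6.3.1 is a closed, cause-restricted list, so non-fatal exercise-test harm and admissions labelled unrelated have no defined route to the team meeting or the suspension rule

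*Combined protocol and SAP*

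**What the plan says.** Section 6.3.1 opens with the termination rule: "Early termination will occur in the case of serious adverse events (SAE) related to study interventions". It then defines the event and its first consequence: "If a SAE occurs (death or hospitalisation of study subject for heart failure or related conditions, device related complications), the study team will meet". Next comes the causality step: "A decision as to whether adverse events are related to study procedures will be made according to clinical judgement by the study group". The suspension rule follows: "If the SAE is deemed to be due to the study intervention, the trial will be immediately suspended pending further investigation".

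Four other places bear on this.

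- Section 6.2 lists the risks of taking part. Besides implantation and radiation it says: "Exercise tests are low risk procedures conferring overall risk of 1 in 10 000 of serious complication".
- Section 5 allows discontinuation on two grounds only: the safety concerns set out later in the document, and failure to recruit in time. Section 6.3.1 is thus the only safety route.
- The Schedule of Evaluations has no adverse-event row, and none of the 19 items in Section 4 is a safety outcome.
- Section 3 places randomisation after the implant ("Following successful device placement, subjects will be randomised in a 1:1 ratio"), and Section 5 sets the analysis population ("Enrolled subjects will be analysed in a per protocol fashion"). Neither states a denominator for adverse events.

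**The concern.** A seriousness definition should say how bad an event is and leave its cause to a later judgement. Here the order is partly reversed. Someone must first decide that an admission was for heart failure or something related to it, with no definition to guide them. Only then does the event count as an SAE and bring the team together. The bracket has no term such as 'including' that would open the list. It also has no general criterion for a life-threatening event, an admission for any cause, or a prolonged stay.

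Two things are at stake. One is participant protection, because the meeting and the suspension rule both depend on the list. The other is the safety information handed to the next trial. This is a feasibility study of an added invasive procedure, and one uncounted patient in 10 moves an observed event rate by 10 percentage points.

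**Working it through.** The plan gives no figure to reproduce on this point. The check is mainly a reading of the text, with arithmetic for scale.

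**Scope of each step in 6.3.1**

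| Step | Kind of event | Related to |
|---|---|---|
| Early termination | SAE | study interventions |
| Team meeting | SAE, as listed in the bracket | not stated |
| Relatedness decision | adverse events | study procedures |
| Suspension | the SAE | the study intervention |

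The relatedness step is wider than the steps on either side of it. An exercise test is plainly a study procedure; whether it is part of the study intervention is not said. An arrhythmia treated at the university site without admission is not a death, a hospitalisation or a device complication. It falls within the wording of the relatedness decision, but nothing brings it there, and the suspension sentence does not clearly reach it.

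**Exercise tests**

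Inputs: 10 patients (2.2.2); two bicycle tests per assessment visit, exercise echocardiography and cardiopulmonary testing (Section 3); three assessment visits (1, 3 and 4), or four with Visit 6; risk 1 in 10 000 (6.2), taken here as per test and independent between tests.

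- Tests: 10 × 2 × 3 = 60; with all patients in the extension, 10 × 2 × 4 = 80.
- P(at least one serious complication) = 1 − (1 − 0.0001)^n.
- n = 60: 0.0060, or 0.6%. n = 80: 0.0080, or 0.8%.
- If the introductory test in 2.11 is separate from the Visit 1 test, there are 10 more tests, which adds about 10 × 0.0001 = 0.1 percentage point.

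**Implantation**

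Section 6.2 puts serious complications at 1% for a dual chamber device and 2% for a biventricular one. P(at least one in 10) = 1 − 0.99^10 = 9.6% and 1 − 0.98^10 = 18.3%. Most of these would count as device related complications, so the list largely covers them.

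**Hospitalisations outside the list**

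The documents give no rate. Let p be the assumed chance that a patient has such an admission during the study. P(at least one in 10) = 1 − (1 − p)^10.

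| Assumed p | P(at least one in 10) |
|---|---|
| 5% | 40% |
| 10% | 65% |
| 20% | 89% |

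If p is read as admission for any cause, these are upper limits, because heart-failure and device admissions are already listed.

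**The case against.** The strongest reply is that this is loose drafting rather than a hole in safety oversight. Several clinicians sit in the study group, and the relatedness sentence already speaks of adverse events and study procedures. An admission for arrhythmia or infarction in a heart-failure patient could well be called a related condition. Events may also surface in other ways: medical examination and medication history at Visits 1, 3, 4 and 6, the telephone consent in 2.8, and case record forms (6.4) whose content is not shown. All of that stands, and it limits the point to the absence of a defined trigger and a defined place to record events.

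Four stronger readings are tempting, and the documents do not support them.

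- A reader might infer that exercise-test harm can never reach the relatedness review. The wording of that review covers it; only the route is missing.
- A reader might infer that suspension cannot follow from exercise-test harm. A death during a test is most naturally covered, since 'death' reads as standing alone, and an admission after a test may be classed as related.
- A reader might use the mortality shares in 1.1 ("including 26% sudden cardiac death, 14% heart failure and 5% myocardial infarction") to argue that a heart-failure filter misses most deaths. That needs the less natural reading in which the qualifier attaches to death. The shares also say nothing about hospitalisation.
- A reader might infer that complications of failed implants are the ones most likely to go uncounted. Device related complications are listed without restriction to randomised patients, failed implantation is part of a secondary objective (2.1), and Section 5 records drop-out reasons at each stage. The per-protocol rule does not remove anyone from safety reporting.

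It is also fair to say that a wider definition lets more events reach an existing suspension rule. That is a real cost.

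**Conclusion.** The point holds in limited form. Followed as written, 6.3.1 gives a non-fatal serious exercise-test event, or an admission labelled unrelated, no defined route to the team meeting or the suspension rule, and Section 5 offers no other safety route. The section's own scopes do not match each other or the risks named in 6.2, so these passages must be reconciled.

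Exercise-test harm is a small part of this: a 0.6% to 0.8% chance of any event, if the quoted risk applies per test. Unlisted hospitalisation matters more, at 40% to 89% for at least one patient in 10, but that range rests wholly on an assumed 5% to 20% per patient. No efficacy estimate is affected.

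**What to change.** 1. In 6.3.1, replace the bracket with a cause-neutral definition: any death, any life-threatening event, any unplanned or prolonged hospitalisation, and any serious complication of implantation, device, programming or exercise testing. Relatedness is judged only afterwards, by the existing study group.
2. Reconcile 'study procedures' and 'study intervention(s)' within 6.3.1, and with the risks in 6.2, so that each step states the same scope. This note proposes no new threshold for suspension or termination.
3. Add an adverse-event row to the Schedule of Evaluations, with collection from the first study test to last contact, using the telephone contact in 2.8.
4. State that event counts are reported over all patients in whom an implant was attempted, whether or not they were randomised.

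The cost is one paragraph, one schedule row and a case record form page. There will be a few more events to review, the reported counts will look less favourable, and more events will be able to reach the existing suspension review.
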